#### **8.1.2. Active Treatment Phase (from Week 16 to 32)**

In addition to permitted concomitant medications and procedures (Section 8.1.1), subjects in the active treatment phase will have the option of adding topical therapies (including, but not limited to, topical corticosteroids, topical retinoids or vitamin D3 analogue preparations) and/or

phototherapy (excluding oral PUVA) to their treatment regimen. Dose modification is permitted for background doses of NSAIDs for PAO and concomitant medications for complication of disease other than PPP.

## 8.2. Prohibited Concomitant Medications and Procedures

### 8.2.1. Double-blind, Placebo-controlled Phase (Week 0 to Week 16)

The following treatment cannot be employed for the duration of the double-blind, placebo-controlled phase:

- Topical therapy
  - Topical therapies that could affect PPP or the efficacy evaluation (including, but not limited to, corticosteroids, retinoid, vitamin D3 derivatives, tacrolimus, antihistamine, antibiotics or traditional Chinese/Japanese herbal preparations).  
*Note: only use of topical antibiotics for the treatment after skin biopsy is permitted.*
- Conventional systemic therapy
  - Systemic therapies that could affect PPP or the efficacy evaluation (including, but not limited to corticosteroids, retinoids, antihistamine, antibiotics, JAK inhibitors, 1,25-dihydroxy vitamin D3 and analogues, psoralens, sulfasalazine, hydroxyurea, dimethyl fumarate, biotin, colchicine or traditional Chinese/Japanese herbal preparations).
- GMA
- Phototherapy
  - UVB or PUVA
- Biologic therapies:
  - TNF $\alpha$  or IL17 blockers such as adalimumab, brodalumab, certolizumab pegol, etanercept, golimumab, infliximab, ixekizumab, secukinumab (or biosimilars for each)
  - Anti-IL12 or anti-IL23 monoclonal antibodies such as guselkumab, ustekinumab or tildrakizumab\* (or biosimilars for each)
  - Other biologics that could affect PPP or the efficacy evaluation
- Treatment for focal infection
  - Focal infection must be carefully assessed in all subjects, and if treatment for focal infection is obviously required, treatment for the focal infection (examples are shown in [Section 4.3](#)) should be completed prior to 24 weeks before baseline.  
Focal infection treatments for PPP below (but not limited to) except for dental therapy (see [Section 8.1.1](#)) at any time during the study.
    - Tonsillectomy for tonsillitis

---

\* Not approved in Japan.

- Endodontic treatment for periapical pathosis
- Periodontal surgery for moderate to severe periodontitis
- Systemic medications for PAO
  - Systemic therapy, including, but not limited to, corticosteroids, bisphosphonates, immunosuppressants [eg, MTX, azathioprine, cyclosporine or 6-thioguanine, mercaptopurine, mycophenolate mofetil, tacrolimus] and other biologics (eg, anti-IL1 antibody).
- Treatment for complication of disease other than PPP
  - Systemic corticosteroids
  - Disease-modifying agents such as MTX, sulfasalazine, or intramuscular (IM) gold are prohibited during the study.
- Use of strong CYP3A4 enzyme inducers (eg, rifampicin, phenobarbital, carbamazepine, phenytoin and St. John's Wort)
  - Coadministration of the strong CYP3A4 enzyme inducer, rifampicin, resulted in a reduction of systemic exposure of apremilast, which may result in a loss of efficacy of apremilast.
- Use of any investigational drug or device
- Prolonged sun exposure or use of tanning booths or other ultraviolet light sources are also not permitted.

### **8.2.2. Active Treatment Phase (from Week 16 to 32)**

Use of medications and procedures except for those described in [Section 8.1.2](#) are not permitted.

### **8.2.3. Observational Follow-up**

There is no restriction of concomitant medication during the observational follow-up phase.

### **8.3. Required Concomitant Medications and Procedures**

Not applicable.

## 9. STATISTICAL CONSIDERATIONS

### 9.1. Overview

This is a 16-week placebo-controlled study, followed by a 16-week active treatment phase to evaluate the efficacy of apremilast (CC-10004) in Japanese subjects with PPP.

The primary efficacy endpoint, PPPASI-50 at Week 16 will be assessed and the apremilast 30 mg BID group will be compared to the placebo group.

The primary analysis will be performed when all subjects complete Week 16. Additionally, an analysis will be performed after all subjects complete the active treatment phase of the study (16 weeks of blinded treatment) and follow-up at Week 32 or discontinue early.

A Statistical analysis plan (SAP), which includes detailed list of analyses, will be written based on this protocol.

### 9.2. Study Population Definitions

The safety population will include all randomized subjects who received at least one dose of IP. The analysis of safety data in this study will be based on the safety population and subjects will be included in the treatment to which they actually received.

The intent-to-treat (ITT) population will be defined as all randomized subjects who received at least one dose of IP. Subjects will be included in the treatment group to which they are randomized.

The per protocol (PP) population will include all subjects in the ITT population who have no protocol deviations that may substantially affect the efficacy results during the 16 weeks placebo-controlled treatment phase. The final determination of protocol deviation criteria to define the PP population will be made prior to the unblinding of the database and will be documented separately.

### 9.3. Sample Size and Power Considerations

A total of approximately 86 subjects will be randomized 1:1 ratio to receive apremilast 30 mg BID or placebo. The study has 80% power (based on a chi-square test at a 2-sided significance level of 0.10) to demonstrate the superiority of apremilast 30 mg BID over placebo with respect to the primary endpoint of PPPASI-50 at Week 16, assuming the PPPASI-50 rates of 45% (apremilast 30 mg BID) and 20% (placebo), respectively. PPPASI-50 rate of 20% at Week 16 in placebo is based on the placebo rate of 21% at Week 16 in guselkumab Phase 2 study ([Terui, 2018](#)). Considering at least 20% difference as a clinically meaningful difference, apremilast 30 mg BID PPPASI rate of 45% is expected in this study. The sample-size was estimated using SAS 9.4 power procedure.

For the skin biopsy RNA expression analysis, N=13 subjects per arm will provide 80% probability to observe the lower limit of the 90% confidence interval (CI) of a decrease of IL8 mRNA expression from baseline to Week 16 in the apremilast treated arm is over -44% , based on the mean and standard deviation (SD) change observed in a 12 weeks apremilast psoriasis study CC-10004-PSOR-004 ([Gottlieb, 2013](#)). For the serum protein biomarker analysis, N=17 subjects per arm will provide 80% probability to observe the lower limit of the 90%CI of an

absolute difference from baseline to Week 16 of IL17A levels in the apremilast arm is over 60%, based on the mean and SD change observed in the psoriasis study in Japan, CC-10004-PSOR-011 ([Gariset, 2018](#)).

## **9.4. Background and Demographic Characteristics**

Subjects' age, weight, height and other continuous demographics and baseline characteristics will be summarized using descriptive statistics (n, mean, median, standard deviation, minimum, and maximum), while gender, race, and other categorical variables will be summarized with frequency tabulations. Medical history data will be summarized using frequency tabulations by system organ class and preferred term.

## **9.5. Subject Disposition**

Subjects disposition (analysis population allocation, entered, completed, discontinued, along with primary reason for discontinuation) will be summarized using frequency and percent by phase. A summary of subjects randomized by site will be provided. Protocol deviations will be summarized using frequency tabulations.

## **9.6. Efficacy Analysis**

### **9.6.1. Efficacy Evaluation for the Primary and Secondary Endpoints**

All efficacy analyses will be performed using the ITT population. In addition, an analysis using the PP population will be provided for the primary efficacy endpoint. The analyses using the ITT population will be considered as the primary analysis.

#### **9.6.1.1. Primary Efficacy Endpoint - (Weeks 0 - 16)**

The primary efficacy endpoint of the proportion of subjects receiving apremilast 30 mg BID or placebo who achieve a PPPASI-50 at Week 16 from baseline will be evaluated.

The primary efficacy endpoint will be analyzed using a chi-square test. The testing will be conducted at the two-sided 0.10 significant level and the two-sided 90% CI for the treatment difference of the PPPASI-50 response rates will be provided. The two-sided 95% CI will also be provided for reference. The primary missing data handling approach for PPPASI-50 responder will be nonresponder imputation (NRI), by which a subject without sufficient data for the response determination will be considered a nonresponder. Sensitivity analysis using the PP population and/or the other missing data handling approach [eg, last observation carried forward (LOCF) method] will be performed and the Cochran-Mantel-Haenszel (CMH) test stratified by the randomization stratification factors [PPPASI total score range ( $\leq 20$  score, 21-30 score,  $\geq 31$  score) and focal infection status (Yes, No) at baseline] will be conducted to support the primary analysis.

#### **9.6.1.2. Secondary Efficacy Endpoints - (Weeks 0 - 16)**

Descriptive statistics will be presented for all secondary endpoints in [Table 2](#). Specifically, for continuous endpoints, descriptive statistics (n, mean, standard deviation, median, minimum, and maximum) for baseline, Week 16 and Week 16 change from baseline will be provided. Binary endpoints will be summarized with frequency tabulations.

Treatment comparisons between the apremilast 30 mg BID and placebo will be performed for the secondary endpoints. Continuous efficacy endpoint will be analyzed using the analysis of covariance (ANCOVA) model adjusted for PPPASI total score range ( $\leq 20$  score, 21-30 score,  $\geq 31$  score) and focal infection status (yes, no) at baseline as factors, and the associated baseline value as covariate, while binary endpoints will be evaluated using the CMH test previously described for the primary endpoint. The primary missing data handling approach for continuous endpoint will be multiple imputation (MI).

Secondary efficacy endpoints will be tested without multiplicity adjustment, therefore the p-value for those endpoints will be regarded as nominal. For secondary efficacy endpoints, the two-sided 95% CI will be provided.

#### **9.6.1.3. Primary and Secondary Endpoints - (Weeks 16 - 32)**

The active treatment phase runs from Week 16 to Week 32. Descriptive statistics will be provided. Specifically, for continuous variables, descriptive statistics (n, mean, standard deviation, median, minimum, and maximum) for baseline, specified time points and changes from baseline will be provided. Categorical variables will be summarized with frequency tabulations.

#### **9.6.1.4. Subgroup Analysis**

Subgroup analyses for comparisons of the proportion of subjects who achieve PPPASI-50 at Week 16 between apremilast 30 mg BID and placebo, based upon baseline demographic, and baseline disease characteristics, will be provided to determine the robustness of the treatment effect.

#### **9.6.2. Efficacy Evaluation for Exploratory Endpoints - (Weeks 0 - 16)**

Descriptive statistics will be presented for exploratory endpoints. Specifically, for continuous variables, descriptive statistics (n, mean, standard deviation, median, minimum, and maximum) for baseline, specified time points and change from baseline will be provided. Categorical variables will be summarized with frequency tabulations.

The Kaplan-Meier procedure will be used to characterize the time to achieve at least PPPASI-50 and PPPASI-75 during the double-blind placebo-controlled phase (Weeks 0-16).

#### **9.6.3. Efficacy Evaluations for Exploratory Endpoints (Weeks 16 - 32)**

The active treatment phase runs from Week 16 to Week 32. Descriptive statistics will be provided. Specifically, for continuous variables, descriptive statistics (n, mean, standard deviation, median, minimum, and maximum) for baseline, specified time points and changes from baseline will be provided. Categorical variables will be summarized with frequency tabulations. These data summaries will be presented according to the treatment sequence received, ie, apremilast 30 mg BID/30 mg BID, or placebo/apremilast 30 mg BID.

### **9.7. Safety Analysis**

The safety analyses will be performed using the Safety population. Safety will be assessed by clinical review of all relevant parameters including TEAEs which are defined as any AEs that

begin or worsen on or after the first dose of IP through 28 days after the last dose of IP, laboratory tests, and vital signs; no inferential testing for statistical significance will be performed. Data from safety assessments will be summarized descriptively for the double-blind, placebo-controlled phase (Weeks 0 to 16) and the apremilast exposure period when subjects receive apremilast treatment. For safety analyses in the active treatment phase, baseline will be relative to the first dose date following randomization at Week 0. For safety analyses in apremilast exposure period, baseline will be relative to the first apremilast dose date at Week 0 for subjects initially randomized to apremilast or Week 16 for subjects initially randomized to placebo and switched to apremilast in the active treatment phase (Weeks 16 to 32).

AEs will be classified using the Medical Dictionary for Regulatory Activities (MedDRA) classification system. All TEAEs will be summarized by system organ class, preferred term, severity, and relationship to IP. AEs leading to death or to discontinuation from treatment and SAEs will also be summarized and listed separately.

Laboratory data will be summarized descriptively. In addition, shift tables showing the number of subjects with values low, normal, and high compared to the normal ranges of pretreatment versus posttreatment will be provided. Associated clinical laboratory parameters such as hepatic enzymes, renal function, and hematology values will be grouped and presented together. Individual subject values will be listed and values outside of the standard reference range will be flagged. Shift tables and analyses of changes from Baseline will be produced. To account for the different exposure to the IP, TEAEs or marked laboratory abnormalities will also be summarized using the exposure-adjusted incidence rate, in addition to the simple incidence rates.

Vital sign measurements, including weight, will be summarized descriptively by visit. In addition, shift tables showing the number of subjects with values low, normal, and high based on the specified ranges pre-treatment versus post-treatment will be provided.

The change from baseline for each of the vital signs including weight will be summarized. Incidence of abnormal vital signs parameters will be tabulated.

The detailed safety analyses will be specified in the SAP.

[figure not shown]
## **9.8. Interim Analysis**

No interim analysis is planned for this study.

## **9.9. Other Topics**

### **9.9.1. Concomitant Therapy**

All concomitant treatments documented during the study period will be summarized in frequency tabulations. The anatomical therapeutic chemical (ATC) coding scheme of the World Health Organization (WHO) will be used to group medications into relevant categories for these tabulations. Separate data summaries of background medications will be provided.

## 10. ADVERSE EVENTS

### 10.1. Monitoring, Recording and Reporting of Adverse Events

An AE is any noxious, unintended, or untoward medical occurrence that may appear or worsen in a subject during the course of a study. It may be a new intercurrent illness, a worsening concomitant illness, an injury, or any concomitant impairment of the subject's health, including laboratory test values (as specified by the criteria in Section 10.3), regardless of etiology. Any worsening (ie, any clinically significant adverse change in the frequency or intensity of a pre-existing condition) should be considered an AE. A diagnosis or syndrome should be recorded on the AE/SAE case report form (CRF) rather than the individual signs or symptoms of the diagnosis or syndrome.

Abuse, withdrawal, sensitivity or toxicity to an IP should be reported as an AE. Overdose, accidental or intentional, whether or not it is associated with an AE should be reported on the overdose CRF. (See Section 7.4 for the definition of overdose.) Any sequela of an accidental or intentional overdose of an IP should be reported as an AE on the AE CRF. If the sequela of an overdose is an SAE, then the sequela must be reported on the paper SAE report form and on the AE CRF. The overdose resulting in the SAE should be identified as the cause of the event on the paper SAE report form and AE CRF but should not be reported as an SAE itself.

In the event of overdose, the subject should be monitored as appropriate and should receive supportive measures as necessary. There is no known specific antidote for apremilast overdose. Actual treatment should depend on the severity of the clinical situation and the judgment and experience of the treating physician.

All subjects will be monitored for AEs during the study. Assessments may include monitoring of any or all of the following parameters: the subject's clinical symptoms, laboratory, pathological, radiological or surgical findings, physical examination findings, or findings from other tests and/or procedures.

All AEs (non-serious and serious) will be recorded by the Investigator from the time the subject signs informed consent until 28 days after the last dose of IP as well as SAEs made known to the Investigator at any time following the protocol-required reporting period or after end of study. All AEs (serious/ non- serious) will be recorded on the CRF and in the subject's source documents. All SAEs must be reported to Amgen Global Patient Safety within 24 hours of the Investigator's knowledge of the event using the paper Serious Adverse Event Report Form (refer to [Appendix J](#)) by facsimile/email of the paper SAE Form directly to Amgen Global PatientSafety.

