### 6.3. Follow-up Period

All subjects will be followed for 28 days after the last dose of IP for AE reporting, as well as any serious adverse events (SAEs) made known to the Investigator at any time thereafter, as described in [Section 10.1](#).

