### **6.3.1. Observational Follow-up Visit**

Observational Follow-up evaluation will be performed on 28 days after last dose of IP. An administrative window of  $\pm$  7 days is permitted.

During the observational follow-up period;

- Subjects must complete all SROs prior to any other study procedure being performed.
- Efficacy assessments may be performed by the qualified physician who has completed the training for efficacy evaluation, but only after the subject has completed all SROs assessments.
- The physician performing efficacy assessments shall make independent observations at a given study visit and shall not review previous assessments in advance of conducting the assessments.

The following evaluations will be performed as specified in the Table of Events ([Table 5](#)):

- Concomitant medications and procedures evaluation
- AE/SAE evaluation (monitored through 28 days after the last dose of IP)
- Psychiatric evaluation
- Vital signs
- Weight
- Limited physical examination
- Clinical laboratory evaluations
  - Hematology/Chemistry
  - Immunology/Inflammation
- Efficacy assessment (see [Section 6.4](#))
  - PPPASI, PPSI, PGA and modified PPPASI
- Subject reported outcomes (see [Section 6.7](#))
  - Subject's VAS assessment for PPP symptom, Subject's assessment for PPP signs/findings

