5.2.1. Analysis Periods

Per protocol specification, data summary and analysis will be provided for the following periods, if appropriate.

- Placebo-controlled Phase/Period

This period starts on the day of randomization (Week 0/Visit 2), and stops on below, whichever is later:

- (1) the day of Week 16/Visit 10 if the subject continued study treatment to the active treatment phase
- (2) the day of the discontinuation if the subject discontinued study treatment prior to or at Week 16/Visit 10
- (3) the last known study day if the subject is lost to follow-up prior to Week 16/Visit 10

CC-10004 (Apremilast)

Statistical Analysis Plan. Protocol CC-10004-PPP-001

The two treatment arms are apremilast 30 mg BID or Placebo.

- Active Treatment Phase/Period

This period starts on one day after the day of the first dose of apremilast at Week 16/Visit 10, and stops on either below.

- (1) the day of Week 32/Visit 14
- (2) the day of the discontinuation if the subject discontinued prior to or at Week 32/Visit 14
- (3) the last known study day if the subject lost to follow-up prior to Week 32/Visit 14 during the phase

The two treatment arms are 30 mg BID/30 mg BID, and Placebo/30 mg BID.

For safety analysis, the period starts on the day of the first dose of apremilast in the period.

- Observational Follow-up Phase/Period

Subjects who complete or discontinue the study treatment, will be followed up for 28 days after last dose of IP.

For adverse event analysis, data from the first 28 days after the last dose of IP will be included in the precedent treatment phase and data after the 28 days will be presented separately.

- Apremilast-exposure Period

This period starts on the date of either:

- (1) the first dose of IP following randomization (Week 0/Visit 2) for subject who are treated with apremilast from Week 0
- (2) the first dose of IP from the IP dispensed at Week16/Visit 10 for subjects who were originally treated with placebo and are switched to apremilast at Week 16

This period stops on either: (1) data restriction date; or (2) the end of the study.

During the apremilast-exposure period, data are presented by treatment sequence, i.e., Placebo/30 mg BID, 30 mg BID as Initiated, and a total column of 30 mg BID as Treated.

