11.1. Adverse Events

Adverse events will be analyzed in terms of treatment-emergent adverse events (TEAEs) which are defined as any AEs that begin or worsen on or after the first dose of IP through 28 days after the last dose of IP or study treatment discontinuation date, whichever is later. All AEs will be classified using the Medical Dictionary for Regulatory Activities (MedDRA) classification

CC-10004 (Apremilast)

Statistical Analysis Plan. Protocol CC-10004-PPP-001

system version 21.1 or higher. Unless otherwise specified, AEs will be summarized by system organ class (SOC) and preferred term (PT), with SOCs presented in the standard international order and PTs within SOCs will be presented in descending order of subject incidence.

A treatment-related TEAE is defined as TEAE which was suspected to be related to the study drugs.

AEs and marked abnormalities will be summarized by subject incidence and EAIR for the placebo-controlled phase (Weeks 0 to 16) and for the Apremilast-exposure period. In addition, selected summaries for the active treatment phase (Weeks 16 to 32) and the observational follow-up phase (4 weeks) will be presented.

An overall summary of the following AE categories will be provided.

- TEAE
- TEAE related to study drug
- Severe TEAE
- Serious TEAE
- Serious TEAE Related to Study Drug
- TEAE leading to dose reduction
- TEAE leading to drug interruption
- TEAE leading to drug withdrawal
- TEAE leading to death

In addition, for apremilast-exposure period overall summary of TEAEs will also be provided.

Tables summarizing the incidence of TEAEs by SOP and/or PT will be generated for each of the following:

- All TEAEs
- Most frequent TEAEs (subject incidence $\geq 5\%$ or another cut-off if justified)
- Treatment-related TEAEs
- TEAEs by maximum severity
- Serious TEAEs and treatment-related serious TEAEs
- TEAE leading to dose reduction
- TEAE leading to drug interruption
- TEAE leading to drug withdrawal
- TEAE leading to death
- First onset and new events of TEAE by exposure interval
 - placebo controlled phase (weeks): ≤ 1 , > 1 to ≤ 2 , > 2 to ≤ 4 , > 4 to ≤ 8 , > 8 to ≤ 12 , > 12 to ≤ 16 , > 16

CC-10004 (Apremilast)

Statistical Analysis Plan. Protocol CC-10004-PPP-001

- apremilast-exposure period (weeks): ≤ 1 , > 1 to ≤ 2 , > 2 to ≤ 4 , > 4 to ≤ 8 , > 8 to ≤ 12 , > 12 to ≤ 16 , > 16 to ≤ 24 , > 24 to ≤ 32 , > 32
- TEAE for the subgroups in [Section 10.4](#)

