14. INTERIM ANALYSIS

No interim analysis is planned prior to the analysis of the primary efficacy endpoint at Week 16.

CC-10004 (Apremilast)

Statistical Analysis Plan. Protocol CC-10004-PPP-001

**15. CHANGES TO THE STATISTICAL ANALYSES SECTION OF
THE PROTOCOL**

No changes to the statistical analyses section of the protocol are made in this SAP.

CC-10004 (Apremilast)

Statistical Analysis Plan. Protocol CC-10004-PPP-001

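### SAP Section 11.1 adds an undeclared, ambiguous end date to the TEAE window, which can then run past Protocol Section 9.7 and past required recording of non-serious AEs (minor)

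*Protocol*

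**What the plan says.** **Collection.** Protocol Section 10.1 has the investigator record all AEs, serious or not, "from the time the subject signs informed consent until 28 days after the last dose of IP as well as SAEs made known" afterwards. Section 6.3 repeats the limit: "All subjects will be followed for 28 days after the last dose of IP for AE reporting". Section 6.3.1 uses the same 28 days for the follow-up visit.

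**Protocol TEAE definition.** Section 9.7 counts AEs that "begin or worsen on or after the first dose of IP through 28 days after the last dose of IP". It gives no alternative end date.

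**SAP TEAE definition.** Section 11.1 runs the window "through 28 days after the last dose of IP or study treatment discontinuation date, whichever is later".

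**SAP allocation of AEs to phases.** Section 5.2.1 says that "data from the first 28 days after the last dose of IP will be included in the precedent treatment phase" and that "data after the 28 days will be presented separately".

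**Declared changes.** SAP Section 15 states: "No changes to the statistical analyses section of the protocol are made in this SAP".

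**The concern.** Protocol Sections 9.7 and 10.1 and SAP Section 5.2.1 all cut at the same day, 28 days after the last dose. SAP Section 11.1 alone can go further, and the SAP does not record this as a departure from the protocol.

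Three things follow for any subject in whom the extension is not empty:

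- **Ascertainment changes inside one table.** Up to day 28 after the last dose all AEs must be recorded. In the extension only SAEs must be, so non-serious events appear only if someone happens to note them.
- **Two SAP sections treat the same event differently.** It carries the TEAE flag under Section 11.1, but Section 5.2.1 takes it out of the treatment phase and presents it separately. The programmer has to decide which governs a by-phase TEAE table.
- **The sentence can be programmed in two ways.** The two readings give different TEAE flags for the same data.

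TEAEs are a named safety endpoint, and safety against placebo is the secondary objective, so the window should be fixed before unblinding and should match the data collected.

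**Working it through.** The plan states no figure on this point, so the check is date arithmetic on the definitions.

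**Inputs**

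- End of required recording of non-serious AEs: last dose + 28 days (Protocol 10.1, 6.3, 6.3.1).
- End of protocol TEAE window: last dose + 28 days (Protocol 9.7).
- Cut for phase allocation: last dose + 28 days (SAP 5.2.1).
- g = discontinuation date minus last dose date, in days. The documents do not give its distribution.

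**Two readings of SAP 11.1, in days after the last dose**

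1. The later of (last dose + 28 days) and the discontinuation date: the window ends at max(28, g), and the overrun is max(0, g − 28).
2. 28 days after the later of the last dose and the discontinuation date: the window ends at 28 + g, and the overrun is g.

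**Can g exceed zero?** Yes. Protocol Section 7.3.1 allows interruption for safety reasons without stating a maximum length. Section 7.8 refers a subject who misses 4 or more consecutive days to a decision on whether dosing resumes, so discontinuation can follow the last dose. SAP Section 17.2.4 treats the last dose date and the discontinuation visit date as separate fields.

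**Largest g between consecutive attended visits** (intervals and allowances from Protocol Table 5), assuming that a stop just after one visit is recorded at the next:

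- To Week 16: 14 + 2 + 2 = 18 days.
- After Week 16: 28 + 4 + 4 = 36 days.

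| g (days) | Protocol 9.7, 10.1, SAP 5.2.1 end | Reading 1 end | Reading 2 end | Overrun, reading 1 | Overrun, reading 2 |
|---|---|---|---|---|---|
| 0 | 28 | 28 | 28 | 0 | 0 |
| 1 | 28 | 28 | 29 | 0 | 1 |
| 14 | 28 | 28 | 42 | 0 | 14 |
| 18 | 28 | 28 | 46 | 0 | 18 |
| 28 | 28 | 28 | 56 | 0 | 28 |
| 29 | 28 | 29 | 57 | 1 | 29 |
| 36 | 28 | 36 | 64 | 8 | 36 |

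On reading 1 there is no overrun in Weeks 0–16 (18 − 28 is negative) and at most 36 − 28 = 8 days after Week 16. A missed visit or a long safety interruption falls outside these bounds. For example, one missed visit before Week 16 gives 28 + 2 + 2 = 32 days, an overrun of 4.

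**Scale, with assumed values.** Suppose 4 early stoppers in an arm (not from the documents). With g = 14, reading 1 gives 0 subject-days and reading 2 gives 4 × 14 = 56. For g from 1 to 18, reading 1 stays at 0 and reading 2 runs from 4 × 1 = 4 to 4 × 18 = 72. Against the 43 × 112 = 4,816 subject-days planned per arm for Weeks 0–16, 72 is about 1.5%.

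**After the fix.** With the clause removed, the SAP window ends at last dose + 28 days and the overrun is 0 for every g.

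**The case against.** The strongest reply is that the clause almost never bites. The natural parse is reading 1, and with visits on schedule that gives nothing in the placebo-controlled phase and at most 8 days afterwards, when every subject is on apremilast. Protocol Section 6.2.1 wants the end-of-treatment evaluation done promptly once the decision to stop is made, and Section 7.8 provides for dosing questions and tablet counts. For subjects lost to follow-up, SAP Section 17.2.4 replaces a completely missing last dose date by the earlier of the last known date and the discontinuation visit date, so it leaves no open-ended gap. This stands, and it is why the point is minor. It does not settle which reading applies, and reading 2 overruns from the first day of any gap.

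Second, the extension is not empty of data. AEs are assessed at early termination and at follow-up, and the follow-up visit may fall as late as day 35 after the last dose. That is true, but capture beyond day 28 is required only for SAEs, so it would be uneven.

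Third, SAP Section 5.2.1 allocates events to phases; it does not define a TEAE. A reader might infer that the SAP holds two rival definitions and that events would be lost. The text does not support that. An event can be flagged as treatment-emergent and still be shown separately, SAP Section 11.1 plans selected follow-up summaries, and non-treatment-emergent AEs are listed. What remains is that the by-phase TEAE tables need one rule.

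Fourth, Protocol Section 9.7 leaves the detailed safety analyses to the SAP, and a wider window is the more inclusive choice. But Section 9.7 itself fixes the TEAE window, so widening it is a change that SAP Section 15 should have listed.

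**Conclusion.** The point holds as a minor inconsistency. SAP Section 11.1 departs from Protocol Section 9.7 without declaring it, can pass the period in which Protocol Section 10.1 requires non-serious AEs to be recorded, and is ambiguous. The overrun is max(0, g − 28) or g days per affected subject, with g unknown. The bounds of zero before Week 16 and 8 days after it rest on reading 1, on visits kept within their allowances, and on no long safety interruption.

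A reader might go further and infer that the TEAE tables in general reach past AE collection, or that the comparison with placebo is biased. The documents support neither. The overrun is conditional on g. On the narrower reading it vanishes in the placebo-controlled phase under the scheduled visit gaps. Nothing in the documents shows that g or early stopping differs by arm; the illustration above assumes no imbalance. The primary efficacy analysis is unaffected, and safety is summarised without inferential testing.

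**What to change.** In SAP Section 11.1, remove the reference to the discontinuation date and the later-of rule from "through 28 days after the last dose of IP or study treatment discontinuation date, whichever is later", so that the TEAE window closes 28 days after the last dose. It then matches Protocol Section 9.7, Protocol Section 10.1 and SAP Section 5.2.1, and SAP Section 15 can stand as written on this point. Later events, mainly SAEs, go into the separate presentation that Section 5.2.1 already provides.

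The cost is one phrase in the SAP. A few late events in early stoppers move out of the TEAE tables but stay visible in the separate presentation and listings. If the sponsor prefers the wider window, the alternative is to state one reading in Section 11.1, declare it in Section 15, and reconcile it with Section 5.2.1 and with the AE recording period. That is more work for little gain.
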